**Exclusion Criteria:**

1. Have undergone any previous peripheral nerve procedures in their affected side, for the treatment of spasticity, including previous cryoneurolysis, chemical neurolysis, neurectomy or arthroplasty.
2. Patients who received botulinum toxin in past 4 months in the same targeted muscles for cryoneurolysis, however, they may enter the study at the 4-month mark.

**Recruitment:**

a) [name], as a physiatrist with expertise in neurorehabilitation of chronic neurological conditions that results in spasticity, will inform all prospective patients that

Effect of the cryoneurolysis on pain and positioning in patients with wrist and hand contracture.

Protocol: [H22-03181]

Version 1.1

Jan 9,2023

are already elected to undergo DNB and cryoneurolysis to advise them that the study is being conducted. With permission, patients or their legal representative will be contacted by the research assistant. The consent form will be offered to the patients when they are offered and selected to undergo a cryoneurolysis. The legal representative will be asked to help with consent process in participants who are physically or cognitively unable to consent. They can either consent at the time of first treatment or at their preference they will have several weeks to review and consider the desire to participate.

b) Recruitment of participants will be through spasticity clinic at Victoria General Hospital, where [name] offers DNB and cryoneurolysis to the patients, routinely, as a part of their standard care to manage pain and spasticity. As a member within the circle of care, he will approach participants regarding obtaining permission for RAs to initiate contact, as per above.

c) Prospective participants will be identified as per the point above.

d) Many of the patients are expected to come from Long Term Care Facilities. We will contact the facility to see if it is easier for our team to do an in facility follow up rather than arranging transport.

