## **Research Design:**

This project constitutes a single-centre, prospective cohort study. Data collection will occur at the Victoria General Hospital (VGH) spasticity clinic. Patients with severe spasticity and contracture are referred to this clinic for different procedures including cryoneurolysis. This study will not interfere or change the patients' medical care. We will do the assessments for the patients who are already candidates for this procedure as a

Effect of the cryoneurolysis on pain and positioning in patients with wrist and hand contracture. 4

Protocol: [H22-03181]

Version 1.1

Jan 9,2023

part of their treatment, besides other provided medical cares and have been accepted to receive it.

All measurements are a part of routine assessment for patients with severe spasticity and contracture.

The evaluation will be done for them after receiving oral and written consent.

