### **Methods:**

The assessment will be done at baseline, 2 weeks, 1 month and 3 months after being enrolled in the study in the same day of their appointments with [name] and includes;

1. Passive and any active range of motions (ROM) of wrist, second and fifth MCP and PIP joints and thumb palmar and radial abduction will be measured by goniometer. Spasticity will be measured based on Modified Ashworth Scale (MAS).
2. The maximum distance between the pulp of the most flexed finger and thumb and the palm of the hand will be measured in centimeter. This distance will be measured during maximal passive extension of the fingers and thumb while the assessor keep the wrist in neutral (or as close to neutral as possible )position.
3. Intensity of pain in the wrist and hand area will be measured by NRS (numerical rating scale), for patients with sufficient cognitive capacity. In this test patients will be asked to score their pain on scale of 0 to 10. Patients who cognitively are not able to score their pain will be assessed by CNPI scale (Checklist of Nonverbal Pain Indicators). In this scale the patient will be observed at rest and during any movement and any nonverbal vocal complaints, facial grimaces, bracing, restlessness, rubbing of the affected area and verbal vocal complaints will be scored accordingly. PI will decide which one of these 2 methods is applicable, based on their assessments, patients' record and in consult with their caregivers.
4. Goal Attainment Scale (GAS): This is a patient-oriented scale to deliver the patient their desired outcomes. Up to 3 individualized, SMART (specific, measurable, achievable, realistic and timed ) goals will be negotiated between participants, caregivers and their physician. At the final visit, they will be asked if they are satisfied with each of these goals and the response will be scored accordingly.

Effect of the cryoneurolysis on pain and positioning in patients with wrist and hand contracture. 5

Protocol: [H22-03181]

Version 1.1

Jan 9,2023

5. Hand hygiene: the evaluator will assess the patients' hands to determine the extent of palm maceration, ulceration or infection; cleanliness of the palm, ease of cleaning and nail trimming; and the effect of hygiene-related disability on other areas of functioning. This assessment is a part of disability assessment scale (DAS). The score ranges from 0 to 3 based on the severity of the maintaining the hand hygiene.

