### **Statistical Analysis:**

A convenience sample of  $n = 25$  patients will be included in this study. This is consistent with existing volumes of consultations to our clinics. Study recruitment will include all patients with wrist and hand contracture that are considered for cryoneurolysis. The outcome measures that we will use are standard clinical measures, but effect sizes are not readily available from previous studies to formally calculate sample size. Furthermore, our study uses an exploratory prospective cohort design, rather than a parallel group trial design, limiting the rationale for providing a sample size calculation.

To assess for statistical significance, a paired t-test on the difference of proportions, applicable to pre-treatment and post-treatment, will be performed. We will employ repeated measures or linear mixed (multilevel) models of change to analyze within-person trajectories in all key outcomes for the intensive repeated measures data spanning the 4-month study period. Such models derive individual parameter estimates for baseline function and change pursuant to nerve or surgical procedure and will directly index the magnitude in improvement for each outcome with everyone serving as their own control (i.e., with change indexed relative to everyone's own personal baseline). If normal distribution in the outcomes does not stand, McNemar's test and

Spearman correlations will be calculated instead of paired t-test and Pearson's correlation, respectively.

The correlation between range of motion and pain score will be reviewed by Pearson's correlation and or Spearman's rank correlation at single time point. The improvement of range of motion or pain scores during two visits will be compared by two sample t test or Wilcoxon rank sum test.

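### The Protocol does not require consent and an untreated baseline before cryoneurolysis, so a patient may enter the cohort after the procedure

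*Protocol*

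**What the plan says.** Recruitment item a) fixes when the form is handed over: "The consent form will be offered to the patients when they are offered and selected to undergo a cryoneurolysis". It then gives two routes to a decision: "They can either consent at the time of first treatment or at their preference they will have several weeks to review and consider". No latest date relative to the procedure is set. The same section mentions both the DNB and cryoneurolysis, and does not say which one is the first treatment.

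Research Design adds that "This study will not interfere or change the patients' medical care" and that "The evaluation will be done for them after receiving oral and written consent". It also says that "All measurements are a part of routine assessment for patients with severe spasticity and contracture".

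Methods sets the visit clock: "The assessment will be done at baseline, 2 weeks, 1 month and 3 months after being enrolled in the study". The clock starts at enrolment, not at the procedure.

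The end of Background and Justification describes the intended patients as people already having cryoneurolysis in the clinic, and adds those enrolled in the group's completed upper extremity study. Exclusion criterion 1 bars anyone with earlier cryoneurolysis on the affected side. Statistical Analysis plans a paired comparison "applicable to pre-treatment and post-treatment, will be performed" and models in which each patient's own baseline is the control.

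**The concern.** The study has no control group, so its evidence is the change from each patient's own baseline. That works only if the baseline is untreated and the decision to take part does not depend on how the treatment turned out. Both conditions need consent and baseline to precede cryoneurolysis, and the Protocol does not fix that order.

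If someone joins after the procedure, one of two things follows. If the first study assessment serves as baseline, some or all of the change has already happened and is lost. If routine pre-procedure values serve as baseline instead, the patient may have chosen to join knowing the result, and satisfied patients may be over-represented. The two errors run in opposite directions. The second also leaves a gap that the data cannot show, namely the patients who declined after a poor result.

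**Working it through.** **1. The text, side by side.** The Protocol gives no figure on this point, so there is none to reproduce. The question is what the stated rules allow.

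| Section | What it fixes | Effect on entry after the procedure |
|---|---|---|
| Recruitment a) | Consent at first treatment, or several weeks to decide | No deadline; first treatment undefined |
| Research Design | Care unchanged by the study | Does not say that the procedure waits for the decision |
| Research Design | Evaluation follows consent | Late consent means a late study baseline |
| Methods | Visits counted from enrolment | Not tied to the procedure date |
| Background | Patients already having the procedure | Points towards treated patients |
| Recruitment a) | Form offered at selection | Points towards earlier entry; sets no deadline for signing |
| Exclusion 1 | No earlier cryoneurolysis on that side | Read literally, bars late joiners; may mean only before the index procedure |
| Statistical Analysis | Pre- versus post-treatment | Needs an untreated baseline; does not provide one |

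Taken together, the rules allow a first study assessment after the procedure. Several weeks is also longer than the first follow-up interval of 2 weeks, so a patient treated in that time could know the result before deciding.

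**2. Size, as an illustration.** Only n = 25 comes from the Protocol. Assumed: true mean change -2.0 NRS points, SD 2.5, normal distribution, all patients scored on the NRS, and a share f of the enrolled patients joining late, with f = 0.2 (25 × 0.2 = 5 patients) or 0.4 (25 × 0.4 = 10 patients).

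*(a) Post-treatment baseline with no further change.* Study mean = (1 - f) × (-2.0).
- f = 0.2: 0.8 × (-2.0) = -1.6
- f = 0.4: 0.6 × (-2.0) = -1.2

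*(b) Routine pre-treatment baseline, joining depends on outcome.* Late deciders join with probability p1 if they did at least as well as the mean, and p2 if not. The shift in their mean is SD × 0.798 × (p1 - p2)/(p1 + p2), where 0.798 is the mean of a standard half-normal.
- 0.9 versus 0.6: 2.5 × 0.798 × 0.3/1.5 = 0.40, so the late joiners' mean is -2.40
- 0.9 versus 0.5: 2.5 × 0.798 × 0.4/1.4 = 0.57, so the late joiners' mean is -2.57

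Study mean = -2.0 - f × shift:

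| | f = 0.2 | f = 0.4 |
|---|---|---|
| 0.9 versus 0.6 | -2.08 | -2.16 |
| 0.9 versus 0.5 | -2.11 | -2.23 |

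With no true effect, the same selection would produce an apparent reduction of 0.2 × 0.40 = 0.08 to 0.4 × 0.57 = 0.23 points.

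**3. Scale.** With 25 patients the standard error of the mean change is about 2.5/√25 = 0.5. The loss under (a), 0.4 to 0.8 points, is of that order. The gain under (b), 0.08 to 0.23 points, is smaller.

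**The case against.** The case on the other side is that entry before the procedure was meant throughout. The design is called prospective, the form is offered at selection, inclusion criterion 5 speaks of candidates, exclusion criterion 1 bars earlier cryoneurolysis on that side, and the analysis is pre- versus post-treatment. The several weeks may simply be the wait between offer and procedure. The entry thresholds (pulp-to-palm distance under 4 cm, MAS of at least 3, refractory pain) would tend to shut out a patient who had clearly improved. Routine measurement means that a pre-procedure record may exist.

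Much of this stands as evidence of intent, and it rules out some stronger readings:
- A reader might infer that treatment goes ahead while the patient decides. The Protocol does not say so. It says only that the study leaves care unchanged.
- A reader might infer that responders will be over-represented. That also requires eligibility to be judged on pre-procedure status while consent comes later, which the Protocol neither states nor rules out.
- A reader might take the late joiners' mean of -2.40 as a 20% overstatement by the study. It applies to late joiners only. At 20% to 40% late joiners the study-level overstatement is 0.08/2.0 = 4% to 0.23/2.0, about 11%.
- A reader might think the damage could never be separated out. Consent and procedure dates, if kept, would identify late joiners, though not the patients who declined after a poor result.

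The objection does not supply the missing rule. An early offer sets no deadline for signing. The word previous in exclusion criterion 1 may mean before the index procedure, and read literally it conflicts with the Background's description of patients already having the procedure. A planned pre/post comparison needs an untreated baseline but cannot create one.

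**Conclusion.** The point holds in a limited form. The Protocol allows, but does not state or intend on its face, that a patient joins after cryoneurolysis. Its sections disagree on whether treated patients can enter, and none requires consent and baseline first. In an uncontrolled study of 25 this matters, because the own-baseline comparison is the only comparison there is.

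On the assumed values, the study mean of -2.0 could be recorded anywhere from -1.2 (post-treatment baselines, 40% late) to about -2.23 (outcome-dependent joining, 40% late). The mean, SD, late share and joining probabilities are all assumptions, and the net direction is unknown. If nobody joins late, there is no bias. The documents do not support a claim that outcome-dependent entry will occur. They support a claim that it is not closed off. This goes beyond missing detail, since consent timing and entry rules belong in the Protocol and a later analysis plan cannot recover a baseline that was never taken.

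**What to change.** - State in Recruitment a) and Research Design that consent is signed and the study baseline completed before cryoneurolysis.
- Define first treatment as either the DNB or cryoneurolysis.
- Give patients the form at or before the DNB visit, so that they keep their several weeks to decide. This changes the sentence that ties the offer to selection for cryoneurolysis.
- Reconcile the end of Background, Research Design, the visit clock in Methods, exclusion criterion 1 and Recruitment a), so that they agree on whether a treated patient can enter.
- Keep a log of eligible patients treated, approached and consented, with consent and procedure dates. Anyone who consents after the procedure is logged and reported separately, and does not count among the 25.

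This governs study entry only and leaves each patient's care as it is. It costs one sentence of rule, some editing and a simple log. A few late deciders would be replaced by later patients, so recruitment may take slightly longer.
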